**With Humira, eow or Methotrexate (as directed)**

eow = every other week

\* For patients not rolling over from Study DE038 or Study M10-444.

\*\* Participation in the registry may be longer if patient switches from MTX arm to HUMIRA arm.

\*\*\* The Direct to HCP Follow-up Process will collect events annually.

The physician will then follow the patient during regular office visits at intervals as information about medications taken for polyarticular JIA will be recorded on the CRF at enrollment and at visits closest to the time points in [Table 1](#). While the physician may deem it appropriate and necessary to have the patient return for additional visits during the observation period, data will be collected via Case Report Forms (CRFs) only at the intervals that most closely correspond to those described in [Table 1](#). However, information related to safety should be captured at any time using the appropriate eCRFs.

Physicians should treat their patients as they would in their routine clinical practice. At any time, patients and physicians may choose to interrupt Humira (monotherapy or combination therapy with MTX) or MTX (monotherapy without Humira) therapy for any reason. Patients that intermittently stop treatment ([Section 10.1](#)) should continue to be monitored during and after their treatment interruption for safety (SAEs and AEs of Special Interest) and effectiveness. These patients will be asked for changes in their polyarticular JIA medications, concomitant medication and medical history at their baseline visit and at their regularly scheduled visits..

Patients that switch from the MTX arm to the Humira arm will be followed as patients in the Humira arm.

If treatment with Humira (monotherapy or combination therapy with MTX) and/or MTX (without Humira) is permanently discontinued for any reason, patients will be encouraged to remain in the registry. The reason for discontinuation should be documented on the eCRF.

Office visits are optional for patients that discontinue treatment, if the patient is not seen at a visit; both active and passive methods will be used to maintain contact. During enrollment, the patient will be asked by the investigator to provide contact information in accordance with local regulations. All patients who are unreachable after 3 consecutive documented attempts to contact the patient via phone, email, or certified letter, will be considered lost to follow-up.

Sites will be asked to check e.g., National Death Index and national/regional cancer registries and vital registries in other countries in accordance with local regulations where accessible. The site will be asked to perform the vital statistic's matching process approximately annually beginning in the second year of the registry, or as soon as data from the NDI and other registries are available to cover the time period of enrollment. Where allowed per local regulations, the sponsor representative may also be requested to perform the vital statistic's matching process.

All Humira and MTX doses will be given using the respective commercially available drug per prescription and physician's recommendation.

The procedures to be conducted in the registry are outlined in [Table 1](#).

**Table 1. Registry Activities**

Procedure	Enrollment Visit (BL)	Month a 1 c , 3 c , 6, 12 b , 18, 24 b , 30, 36 b , 42, 48 b , 54, 60 b	Month 72, 84, 96, 108, 120	At Time of Reported Event
Informed Consent/Patient Authorization d				
Demographics, including Biological Parent Height)				
Medical/Surgical Hx (including JIA Medical/ Surgical Hx and tobacco and alcohol use)				
Pre-Registry Exposure to Humira e				
Vital Signs and Growth Assessment/ Tanner Maturation Staging b				
Safety Data Collection (AEs of Special Interest/SAEs) f				
Previous JIA therapies				
Concomitant JIA therapies				
Concomitant medications at time of reported SAE or AE of interest				
Laboratory Assessments g				
Physician Global Assessment (VAS)				
Parent's Global Assessment (VAS)				
DICHAQ				
CHQ-PF50				
Joint Assessment				
Inactive/Active Disease Status				
Eye Disease (Uveitis) Assessment				
Humira Treatment and Dosing Changes				
MTX Registry Treatment and Dosing Changes				
Case Report Form Completion				
70-Day Follow Up Call h				

- a. Data collection at regular visits that are closest to time points described. For patients participating in the HCP questionnaire process, follow-up is annually.
- b. Tanner Maturation Staging should be completed annually through Year 5, as applicable.
- c. Patients that have not rolled over from AbbVie Study DE038 or Study M10-444 will have additional visits at Month 1 and 3.
- d. Patients that switch from the MTX arm to the Humira arm must be re-consented.
- e. Medical assessments from the first dose of commercial Humira will be collected to enter into this registry.

**Table 1. Registry Activities (Continued)**

- f. AESI, SAEs and pregnancies will be collected from Year 1 through Year 5. From Year 6 through Year 10 SAEs, a subset of AESI that includes congestive heart failure (CHF), malignancies, AEs at least possibly related to and/or leading to discontinuation of registry treatment and pregnancies will be collected. For patients that participate in the direct to HCP follow-up process AESI, hospitalizations, surgeries, and death will be collected annually from Year 1 through Year 5 and malignancies, CHF, hospitalizations, surgeries and death will be collected annually from Year 6 to Year 10. For polyarticular JIA patients from 2 to < 4 years of age while in the registry AESI, SAEs and pregnancies will be collected through Year 10 and those who participate in the direct to HCP follow-up process will have AESI, hospitalizations, surgeries and death collected annually through Year 10.
- g. Provide local lab values including but not limited to ESR, CRP, anti-nuclear antibody (ANA), and any labs related to SAE's or AEs of Special Interest (i.e., CPK, presence of lupus anticoagulants or anticardiolin antibodies). The assessments will be collected at baseline and afterwards only when part of physician's site routine care.
- h. Patients who develop an Adverse Event of Special Interest (AESI) or SAE while in the registry will be followed throughout the patient's participation in the registry or direct to HCP follow-up process until satisfactory conclusion or until 70 days following the last registry dose (whichever is longer). Follow-up received on ongoing SAEs and/or AESI post registry conclusion should be reported using standard Post Marketing Reporting.

The procedures outlined in [Table 1](#) are discussed in detail in this section, the exception of the collection of AE information, which is discussed in [Section 7.1.1](#) and Informed consent/patient authorization which is discussed in [Section 8.0](#). For patients participating in the HCP follow-up process, follow-up is done annually as defined in the protocol and only AESI, surgeries, hospitalizations, and death are collected through completion of Year 5. Starting from Year 6 from initial registry enrollment, patients participating in the HCP questionnaire process will be followed annually for congestive heart failure, malignancies, hospitalizations, surgeries, and death through Year 10 ([Figure 1](#)). For polyarticular JIA patients 2 to < 4 years of age in countries with available local approval for this group of patients at the time of consent to the registry and participating in the HCP follow-up process will have AESI, hospitalizations, surgeries and deaths collected for the full 10 years as defined by the protocol ([Figure 2](#)). Any other AEs, SAEs, and/or pregnancies should be reported according to normal spontaneous reporting procedures, and they are not subject to the requirements of this protocol.

### **6.6.1 Demographics**

The physician will obtain patient demographic information at the enrollment visit and record it on the Baseline eCRF. The demographic information will include date of birth,

sex, race, and ethnicity (according to local regulations). Demographic data will not be captured for patients rolling over from a previous Humira (adalimumab) study as this information has already been collected. Only the patient number from the previous clinical study will be recorded in the eCRF required.

Parental heights will be requested from the biological parents, upon consent, which will be used in the analysis of the patient's growth assessment.

### **6.6.2 Medical History**

A complete non-polyarticular JIA related medical and surgical history as well as a history of tobacco and alcohol use will be obtained from each patient at the enrollment visit. A list of each patient's specific polyarticular JIA related medical and surgical history should be recorded in addition to the disease category, activity and the disease onset. For patients rolling over from a previous Humira clinical study, any ongoing AEs and SAEs as well as medical conditions requiring concomitant medication treatment will be captured as medical history items. The onset type of the disease will be recorded, if available, while a detailed medical history will not be required, unless information was omitted upon entry to the prior AbbVie Humira clinical study.

Patients will be asked to provide retrospective SAEs, Adverse Events of Special Interest, and exposure to MTX and/or Humira data, if available upon consent, from the first dose of MTX and/or commercial Humira to entry into this registry.

### **6.6.3 Vitals, Growth Assessments and Tanner Staging**

Vitals including blood pressure, pulse, temperature, will be recorded at Baseline and at each visit through Year 5. Growth assessments, including height and weight, will be recorded at Baseline and at each visit through Year 5 and Tanner Maturation Staging ([Appendix H](#)) will be recorded at Baseline and every 12 months thereafter through Year 5. Biological parent's height will also be collected at the Baseline Visit if consent was obtained.

#### **6.6.4 Prior and Concomitant Medications**

Any DMARD and biologic treatments previously administered and the reason for discontinuation (i.e., AE, lack of effectiveness, intolerance or other) will be recorded. Information on the highest maintained dose, date of last administration, length of time on the medication and reason for stopping the medication will be collected in the source documents and appropriate eCRF pages.

Any medication or vaccine (including over-the-counter or prescription medicines, vitamins and/or herbal supplements) that the patient is receiving at the time of screening, and/or receives during the registry, must be recorded along with the reason for use, date(s) of administration including start and end dates, and dosage information including dose, route and frequency on the appropriate eCRF.

Intra-articular and/or soft-tissue corticosteroid injections must be captured, however the joint that is injected should be considered non-evaluable for 3 months thereafter.

Kineret® (anakinra), Orencia® (abatacept), Rituxan® (rituximab), Enbrel® (etanercept), Remicade® (infliximab) or other approved biologic agents are not to be given concurrently while participating in the registry as per the labeling for MTX and Humira.

Patients should not be enrolled into the MTX arm if they have had prior treatment with any investigational agents or anti-rheumatic biologic therapies such as, but not limited to, Orencia® (abatacept), Enbrel® (etanercept), Remicade® (infliximab), Rituxan® (rituximab), or Actemra® (tocilizumab). Patients in the MTX arm may be prescribed and treated with MTX alone, or in combination with other DMARDs but not with anti-TNFs or other biologic therapies at the time of enrollment.

Patients in MTX arm that require treatment with the biologic/anti-TNF will be excluded from the MTX treatment arm but may continue within the registry. After the Humira treatment arm enrollment is complete, if a patient in MTX treatment arm begins Humira therapy, Humira will be considered a concomitant medication.

Except for live vaccines, patients may still receive vaccines while on Humira. It is recommended that children with JIA be brought up to date with all immunizations prior to starting Humira.

The AbbVie Study Designated Physician identified in Section 7.1.8 should be contacted if there are any questions regarding concomitant or prior therapies.

In addition for patient's age  $\geq$  30 with a reported malignancy event, prior exposure to, or current use of antineoplastics, or other drugs which have a risk of malignancy as stated in their label and other relevant dosing information to estimate total exposure will be collected in the source documents and appropriate eCRF pages. At the time of the reported malignancy adverse event, sites will be asked if any of the prior and concomitant medications contributed to the event. Any medications used prior to the registry will be captured on the appropriate eCRF. Information on the reason for use, date(s) of administration including start and end dates, highest maintained dose, dosage information including dose, route and frequency, and reason for stopping the medication will be collected in the source documents and appropriate eCRF pages.

During registry participation, patients should not be enrolled into any interventional clinical trials.

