After the registry enrollment period is closed to the Humira arm, patients wishing to switch to Humira will be discontinued from the MTX treatment arm; however, the patient will be encouraged to remain in the registry and efforts will be made to follow these patients through Year 10 to gather safety data.

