## **6.2 Patient Follow-up Criteria – HCP Process**

Patients who discontinue full registry participation prior to completing the registry 10 years of follow-up will be offered to participate in the direct to HCP (Health Care Provider) follow-up process, as allowed by applicable local regulations. In order to participate in the direct to HCP follow-up process, the parent or guardian of the patient must sign and date the consent/patient authorization form. Pediatric patients will be included in all discussions as per applicable local regulations in order to obtain verbal or written assent. Patients participating in the HCP follow-up process may not switch registry treatment arms during the HCP follow-up process. To switch to the Humira arm (add on or switch to Humira), an MTX patient following the direct to HCP follow-up process must re-consent at a registry investigative site. The treatment arm at the time of patient authorization will be noted. All data collected post authorization will be included in analysis of the treatment arm indicated at the time of patient authorization, or until the date the patient re-consents in the registry.

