**Figure 3. Treatment Period and Treatment Interruption (TI) Period**

## 10.2 Demographics and Registry Enrollment Characteristics

Baseline characteristics: age, sex, race/ethnicity, weight, height, duration of JIA, JIA disease activity and onset type of JIA Disease onset, Rheumatoid factor (RF+, RF-), HLA-B27, body mass index (BMI), prior therapies for JIA, concomitant polyarticular JIA medications, and Humira dosage and exposure duration.

Demographics and baseline characteristics will be summarized for the All Treated Patient Population. Descriptive statistics for demographics, effectiveness, and safety parameters will be presented. Number of patients with non missing values, mean, and standard deviation will be provided for continuous variables. Counts and percentages will be provided for categorical variables. The number and percentage of patients who discontinue from the registry will be summarized, overall and by reason for discontinuation. Duration of observation in the registry, registry exposure duration and total exposure duration will be summarized as follows:

Duration of observation period = the last date of registry participation (inclusive of HCP process) – enrollment date to MTX or Humira in the registry + 1

Registry exposure duration:

(MTX arm) = last MTX dose date in the registry or the first Humira dose date in the registry whichever is earlier – first MTX dose date in the registry + 1 (The first MTX dose in the registry will be on or after the enrollment date).

(Humira arm) = last Humira dose date in the registry – first Humira dose date in the registry + 14 days – total days of any treatment interruptions (The first Humira dose in the registry will be on or after the enrollment date).

Total exposure duration:

(MTX arm) = last MTX dose in the registry or the first Humira dose date in the registry whichever is earlier – first recorded MTX dose (initial dose) + 1.

(Humira arm) = last Humira dose date in the registry – first recorded Humira dose (initial dose) + 14 – total days of any treatment interruptions. For patients who rolled over from Study DE038 and were in the Placebo arm during the double-blind period of this study, the duration of the double-blind period will be subtracted from total exposure.

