### **10.3.1 Analysis of Observational SAEs and AEs of Special Interest**

The number and percent of patients experiencing SAEs and AEs of Special Interest during the registry, regardless of whether the AEs are reported during or after the Humira or MTX treatment, will be tabulated by body system and Medical Dictionary for Drug Regulatory Activities (MedDRA®) preferred term. Rates (event per 100 patient year of observation) of SAEs and AEs of Special Interest and the 95% confidence interval will be provided. The AEs summaries will also include SAEs and AEs of Special Interest collected through the HCP process. The last contact date is defined as the last date of registry or direct to HCP process participation, whichever occurs later.

The summaries will be provided using data from the first day in registry through the last contact irrespective of drug treatment duration.

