### **10.3.2 Analysis of Registry Treatment-Emergent SAEs and AEs of Special Interest**

Registry Treatment-emergent SAEs and AEs of Special Interest will be summarized.

Registry Treatment-emergent AEs includes AEs occurring from the first dose day of the registry to 70 days after the last dose of registry drug excluding AEs occurring during TI period. The SAEs and AEs of Special Interest collected through the HCP process will not be included in this summary.

The number and percentage of patients experiencing registry treatment-emergent SAEs and AEs of Special Interest will be tabulated by body system and MedDRA® preferred

term. In addition, a summary of SAEs and AEs of Special Interest by severity and relationship to registry drug will be presented. Rates (event per 100 patient-years of registry exposure to Humira or MTX) of SAEs and AEs of Special Interest and the 95% confidence interval will be provided.

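### The observational MTX rate has no cut at a first Humira dose, and the MTX treatment-emergent event window can outlast its person-time

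*Supplement*

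**What the plan says.** **Arm membership after the Humira arm closes.** Section 6.1 says that "patients wishing to switch to Humira will be discontinued from the MTX treatment arm", but also that "efforts will be made to follow these patients through Year 10 to gather safety data". Section 6.6.4 first agrees: "Patients in MTX arm that require treatment with the biologic/anti-TNF will be excluded from the MTX treatment arm but may continue within the registry". Its next sentence still speaks of someone in the MTX arm: "if a patient in MTX treatment arm begins Humira therapy, Humira will be considered a concomitant medication".

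**Direct-to-HCP follow-up.** Section 6.2: "All data collected post authorization will be included in analysis of the treatment arm indicated at the time of patient authorization". The rule ends only if the patient re-consents in the registry.

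**Observational summary.** Section 10.3.1: "The summaries will be provided using data from the first day in registry through the last contact irrespective of drug treatment duration". Events from the HCP process are included. The denominator in Section 10.2 starts from "Duration of observation period = the last date of registry participation (inclusive of HCP process", less the enrolment date, plus one day.

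**Treatment-emergent summaries.** Section 10.2 ends MTX registry exposure and MTX total exposure at the earlier of the last MTX dose and the first Humira dose in the registry. The event window in Section 10.3.2 is set differently: "Registry Treatment-emergent AEs includes AEs occurring from the first dose day of the registry to 70 days after the last dose of registry drug". Section 10.3.3 uses the same end point. Both leave out HCP events and events during treatment interruptions, which are defined for Humira only.

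**The concern.** Section 5.0 makes MTX the reference group for the primary objective, long-term Humira safety. If patients counted as MTX are taking Humira for part of their follow-up, the reference rate is a mixture. Where Humira raises a rate, the mixture lies closer to the Humira-arm rate and the contrast shrinks.

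This matters most in the observational table. Of the overall by-arm summaries, it alone runs beyond 70 days after the last dose and includes HCP data. Section 10.6 adds five years of follow-up because malignancy and heart failure are infrequent, and it is in long follow-up that late Humira starts accumulate.

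The treatment-emergent tables raise a different problem. A patient who adds Humira to continuing MTX stops contributing MTX person-time but, as worded, keeps an open MTX event window. Section 6.1 itself foresees MTX patients who need combination treatment with Humira.

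**Working it through.** **1. The plan's own figure.** Section 10.6 states about 97% power for 4.8 against 2.8 serious infectious events per 100 patient-years (PY), with 1,500 Humira PY and two-sided alpha 0.05. Expected events are 1,500 × 0.028 = 42 and 1,500 × 0.048 = 72. Normal approximation: (72 − 42 − 1.96 × √42)/√72 = 2.04, so power is 97.9%. The exact Poisson test (reject at 56 or more, or 29 or fewer) gives 97.8%. The figure reproduces. It tests the Humira arm against the Study DE038 rate and does not use the MTX arm, so nothing below changes it.

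**2. Where each group is counted.**

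| MTX patient who starts Humira | Arm for analysis | Observational time and events | MTX exposure denominator |
|---|---|---|---|
| While Humira enrolment is open, with re-consent | Humira from re-consent (6.1, 6.2) | Naturally read as ending at the switch | Ends at first Humira dose |
| After closure, still in registry | Conflict: 6.1 and one sentence of 6.6.4 against the next | To last contact, no cut | Ends at first Humira dose |
| In HCP follow-up, no re-consent | MTX (6.2) | To last contact, no cut | Ends at first Humira dose in the registry; HCP events excluded |

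The last column assumes that a Humira dose recorded as a concomitant medication still counts as a Humira dose in the registry.

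**3. Effect on the observational MTX rate.** The share f of MTX-arm time spent on Humira is not given, so it is assumed. The planning rates serve only as illustration: 2.8 off Humira and 4.8 on Humira. MTX rate = 2.8(1 − f) + 4.8f; rate ratio = 4.8/MTX rate.

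| f | MTX rate per 100 PY | Rate ratio |
|---|---|---|
| 0 | 2.8 | 1.71 |
| 10% | 3.0 | 1.60 |
| 20% | 3.2 | 1.50 |
| 30% | 3.4 | 1.41 |
| 40% | 3.6 | 1.33 |

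**4. What would produce such shares.** If a proportion p starts Humira at year s and all are followed for 10 years, f = p(10 − s)/10. Then 20% starting at Year 5 gives 10%; 40% at Year 2 gives 32%; 50% at Year 2 gives 40%. Dropout lowers this. Suppose the 68% in Section 10.6 is exponential loss from follow-up over five years, so the hazard is −ln(0.32)/5 = 0.228 per year. Mean follow-up over 10 years is (1 − e^−2.28)/0.228 = 3.94 years, of which 2.33 fall after Year 2. One third starting at Year 2 then gives f = 2.33/3.94/3 = 20% (ratio 1.50), against 26% (ratio 1.44) with full follow-up. One third starting at Year 4 gives 11% (ratio 1.59).

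**5. Treatment-emergent mismatch.** Assume five years on MTX, with Humira added at Year 3 in 20% of patients. Mean MTX person-time is 0.8 × 5 + 0.2 × 3 = 4.6 years. Mean events counted are 4.6 × 0.028 + 0.2 × 2 × 0.048 = 0.148. The apparent rate is 0.148/4.6 = 3.22 per 100 PY instead of 2.8. With 40% adding Humira it is (4.2 × 0.028 + 0.4 × 2 × 0.048)/4.2 = 3.71.

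**The case against.** The strongest reply is that the protocol says twice that these patients leave the MTX arm, so their later data should not be MTX data. That is a fair reading, and it rules out saying that the protocol plainly keeps post-closure starters in the MTX arm. It does not settle the matter: they are followed to Year 10, the next sentence of 6.6.4 treats them as MTX-arm patients, and no table is assigned to them. For HCP follow-up the assignment to the arm at authorization is explicit. The concomitant-medication wording, for its part, covers only starts after Humira enrolment is complete.

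A reader might also infer that all MTX reference rates contain Humira time. They do not: the treatment-emergent denominators stop at the first Humira dose, and HCP events are excluded there. Nor do the documents support the same charge for patients who switch while enrolment is open. They leave the MTX arm, consent as new patients, and their follow-up restarts; at most the observation formula could say so more plainly.

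The event-window mismatch depends on reading continuing MTX as still being registry drug after Humira is added. A separate SAP, mentioned in Section 10.4.1.4 but not among the documents, might align the window. It could not censor HCP data at a first Humira dose without departing from Section 6.2.

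Finally, no between-arm test or rate ratio is planned, and the treatment-emergent tables also capture malignancy and heart failure in patients still on drug through Year 10. Both points stand and limit the consequence to a descriptive contrast.

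**Conclusion.** The point holds for the observational summary: the MTX rate can include events and person-years on Humira, by explicit rule in HCP follow-up and through unreconciled text for post-closure starters. If Humira raises a rate, the contrast is pulled toward no difference; if it does not, there is no such pull.

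The size cannot be derived from the protocol. The range 1.60 to 1.33, from 1.71, rests on an assumed 10% to 40% exposed share and on serious-infection planning rates. The 2.8 comes from Study DE038, a Humira trial, and is not an MTX rate; malignancy and heart failure rates will differ. Because patients can move to the Humira arm while enrolment is open, and Section 10.6 plans for three years of enrolment, a Year 2 start under the post-closure rule fits only later enrollees. The lower end of the exposed share is therefore the safer guide for that group.

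The treatment-emergent mismatch is a second, separate defect of wording. It would raise the MTX rate through unmatched events, not through Humira person-time in the denominator.

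**What to change.** 1. Reconcile Sections 6.1 and 6.6.4 on the analysis arm of MTX patients who start Humira after closure, and amend the analysis rule in 6.2 to match.
2. In 10.3.1, with the observation formula in 10.2, close MTX events and person-years at the first Humira dose, including one recorded as a concomitant medication, and at the start of another biologic where that date is known. Report later time and events as a separate group, MTX then Humira, including HCP data. Keep the as-enrolled table as a sensitivity analysis.
3. In 10.3.2 and 10.3.3, end the MTX event window at the earlier of the last MTX dose plus 70 days and the first Humira dose, consistent with the exposure formula.

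The cost is analysis wording and one extra column. Humira and MTX dates are already collected on site through Year 10 (6.6.11) and annually from HCPs (7.3). For other biologics, 7.3 asks HCPs about use but ties start and stop dates to Humira and MTX, so that cut will sometimes be unavailable. The MTX arm loses person-years: at a given rate its standard error grows by 1/√(1 − f), about 5% at f = 10% and 29% at f = 40%.
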